2.11.1.3. Hypothalamic dysfunction

Symptoms related to hypothalamic dysfunction, such as obesity, behavioral changes, disturbed circadian rhythm, sleep irregularities, daytime sleepiness, and imbalances in regulation of body temperature, thirst, heart rate and/or blood pressure have been found at diagnosis in 35% of childhood craniopharyngioma patients [136]. The rate of hypothalamic dysfunction dramatically increases following radical surgical treatment - in some series up to 65 to 80% [136, 140]. Even though pre-surgical evaluation of hypothalamic damage is difficult, both clinically and radiologically [137], tumor involvement of the 3rd ventricle or obstructive hydrocephalus are suggestive findings [22]. A three-level clinical grading system for hypothalamic dysfunction has been suggested based on the degree of obesity and hypothalamic tumor involvement [139].

Associated with high morbidity, suprachiasmatic lesions with hypothalamic involvement are difficult to treat. Surgical removal of tumor tissue beyond the mammillary bodies (i.e., in the posterior hypothalamic area) endangers hypothalamic structures and may cause hypothalamic obesity [40, 64]. With the aid of imaging studies, several reports have indicated that the degree of obesity of affected childhood craniopharyngioma patients is positively correlated with the degree and extent of hypothalamic damage [64, 156-158]. Fjalldal *et al.* [159] recently published the results of a cross sectional study of 42 patients who were analyzed for cognitive performance and psychosocial health at a median follow-up of 20 yrs (1 to 40 yrs) after diagnosis of childhood craniopharyngioma. The authors observed disturbed attention and impaired processing speed in craniopharyngioma patients; not surprisingly, the deficits were most pronounced in patients with hypothalamic involvement of childhood-onset craniopharyngioma [159]. Taking these considerations into account, a novel classification of pre-surgical involvement and postsurgical lesions of hypothalamic structures based on magnetic resonance imaging has been recently published [37]. The classification is intended to help establish more risk adapted surgical strategies based on a grading of pre-surgical hypothalamic involvement and postsurgical hypothalamic lesions.

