2.11.1.4. Obesity and eating disorders

Rapid weight gain and severe obesity are the most perplexing complications due to hypothalamic involvement and/or treatment-related hypothalamic damage in craniopharyngioma patients. Weight gain in childhood craniopharyngioma patients often occurs yrs before diagnosis [26], with 12 to 19% of patients reported to be obese at diagnosis [23, 24, 140, 142]. Weight gain occurs despite adequate endocrine replacement of pituitary hormone deficiencies. The hypothalamic disturbance in energy management contributes to the development of severe obesity and is exacerbated by factors limiting physical activity such as marked daytime sleepiness, disturbances of circadian rhythms, and neurological deficits [160]. The degree of obesity frequently increases early after treatment and rapid weight gain frequently occurs during the first 6 to 12 month after treatment [142, 155, 157]. Following treatment, the prevalence of severe obesity is higher, reaching up to 55% [24, 140-142, 150, 155, 161-163]. Obesity and eating disorders result in increased risks of metabolic syndrome [150] and cardiovascular disease [158], including sudden death events [164], increased multisystem morbidity [144], and increased mortality [77, 140, 165-171].

Although the relation of severe obesity with hypothalamic lesions is obvious in craniopharyngioma patients [157, 158, 172], the mechanisms responsible for increased prevalence of cardiometabolic complications in these patients are still unclear. It is likely that in cases of suprasellar extension, hypothalamic function will be compromised and will remain compromised to a certain extent when treated surgically or with irradiation. Although it is a relatively small structure of only 4 ml volume, the

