2.11.1.10. Quality of life, neurocognitive outcome and psychosocial functioning

QoL in craniopharyngioma patients can be affected by both the tumor itself and the treatment received. Reports assessing psychosocial and physical functioning show variable results, ranging from excellent in a majority of subjects to impaired function in almost half of the patients [24, 140, 214-217]. The most common areas of difficulty reported include social and emotional functioning, with patients rating their psychosocial status to be lower than their physical health [140]. Other reported challenges included somatic complaints such as reduced mobility, pain, and self-care [52, 140]. Behavioral questionnaires indicate a high rate of psychopathological symptoms, including depression, withdrawal, and anxiety. The most frequent problems in children's everyday functioning include difficulties in learning, inability to control emotions, unsatisfactory peer relationships, and concerns regarding physical appearance and body image [148, 218].

Reported factors associated with worsening quality of survival outcomes as well as neurocognitive and psychosocial functioning include younger age at diagnosis and preoperative functional impairment. Furthermore, tumor characteristics - including larger tumor volume, hypothalamic and 3rd ventricle involvement at presentation - are reported in the literature to complicate both pre- and post-surgical conditions and therefore survival and QoL outcomes in these patients [33, 40, 139, 219]. Treatment strategies have also been implicated with worse outcomes for surgery alone compared to limited surgery followed by irradiation and for multiple operations for tumor recurrence. Endocrine, neurological, and ophthalmological sequelae all adversely affect QoL outcome [24, 52, 136, 137, 140, 214, 215]. Hypothalamic dysfunction has been found to have the most important negative impact on social functioning, physical ability, and body image [140, 155, 215].

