3.1. Background

HIT-ENDO and KRANIOPHARYNGEOM 2000/2007

Based on the KRANIOPHARYNGEOM 2000/2007 results as well as published results of collaborative studies in connection with HIT-ENDO and KRANIOPHARYNGEOM 2000/2007, the following conclusions can be made:

- Hypothalamic involvement resulting in radical surgical procedures and hypothalamic lesions are both clear predictors for impairments in postoperative functional capacities and QoL [33, 64].
- Considering the long-term consequences in cases of craniopharyngiomas with hypothalamic involvement, it appears that intended radical neurosurgery is **not** advisable [301].
- Patient QoL is seriously impaired in ca. 50% of craniopharyngioma cases due to damage-induced hypothalamic obesity [40, 302].
- Patients with severe obesity presented reduced long-term functional capacities following multiple neurosurgical interventions in the course of treating the disease [215, 217].
- The most significant increase in BMI in patients at risk for obesity occurs during the first 12 month after diagnosis/surgery [155].

Patients with hypothalamic involvement should be classified as high risk regarding long-term consequences and impaired long-term prognosis based on the results of the above-mentioned analyses. There is consensus that complete resections are to be avoided for hypothalamic involved tumors based on the known, long-term consequences.

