4.2. Statistical endpoints and independent variables

The present protocol is a prospective, multicenter registry with the goal to observe and analyse multidisciplinary treatment approaches in childhood-onset craniopharyngioma. Therefore, several endpoints were chosen that reflect patients' survival and QoL. The association between these endpoints and a set of independent variables that represent diagnostic characteristics and treatment strategies will be analysed. On the basis of previous analyses (e.g., KRANIOPHARYNGEOM 2000 / KRANIOPHARYNGEOM 2007), the independent variables have been divided into two categories according to their expected influence on outcome and prognosis of childhood-onset craniopharyngioma.

Endpoints: - Overall survival (OS) defined as time from diagnosis to death

- Progression-free survival (PFS) defined as time from diagnosis to progression or death (whichever occurs first)
- Quality of life (PedQol, PedsQL, FMH)
- Degree of obesity (BMI SDS)

Factors of influence (mandatory):

- Tumor location (grade of hypothalamic involvement, grade 0-2)
- Neurosurgical treatment strategy (intended radical resection vs.
- incomplete resection + XRT)
- Realized degree of surgical resection (complete resection vs. incomplete resection)
- Postsurgical hypothalamic lesions (grade 0-2)
- Irradiation: modality (photon vs. proton beam therapy) and treatment (dose)

Factors of influence (potential):

- Clinical manifestations and symptoms in history
- Duration of history
- Histology (adamantinomatous vs. papillary type)
- Hydrocephalus at diagnosis
- Patient load of treating neurosurgical units (based on patient load during 10 yrs)
- Patient load of treating radiotherapy units (based on patient load dring 5 or 10 yrs)
- Tumor structure in imaging (tumor volume, cysts, calcifications)
- Endocrine deficiencies (number of deficient hypothalamic-pituitary axes)
- Growth hormone substitution (patient age at initiation, duration)
- Ophthalmological deficits (visual acuity, perimetric deficits)
- Neuropsychological findings, memory deficits, cognition (HIT-Basisdiagnostikum)

- Eating disorders (IEG)
- Experimental therapeutic approaches for obesity treatment (GLP-1R Agonists, Oxytocin)
- Other experimental therapeutic approaches, e.g. intracavitary therapy (intracystic IFN- α)

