4.3. Statistical analysis

The analysis of the data collected in this registry will be mainly descriptive. All inferential analyses will be regarded as exploratory (hypotheses generating) and will be interpreted accordingly. The aim of the analyses is to describe the frequency and modality of treatment approaches and to investigate their influence on survival and QoL. Since the planned study is a purely observational study, no randomized comparisons of treatment strategies are possible. Therefore, in addition to univariable analyses, multivariable analysis strategies are used to take account of different baseline risks due to different demographic or diagnostic characteristics. The model selection in the mutivariable analyses can be done by clinical considerations or by means of automated selection as likelihood-ratio based stepwise selection procedures.

Continuous variables (e.g., BMI SDS, QoL) will be summarised using the following descriptive statistics: n (non-missing sample size), number of missing values, mean, standard deviation, median, Q25%, Q75%, maximum and minimum. Histograms or boxplots will be used for graphical presentation of data. For the comparison of independent groups, statistical tests appropriate to the statistical distribution of the particular endpoint will be used (e.g., Student's t-test, Mann-Whintey U-test). To assess the difference of measurements between two different time points, statistical tests as Student's t-test for paired samples, Wilcoxon signed-rank test, or the sign-test will be applied. For comparison of more than two successive measurements, methods accounting for intra-individual correlation will be used (e.g., Linear Mixed Models), additionally adjusting for potential confounders.

Time-to-event endpoints as OS and PFS will be analysed descriptively using the Kaplan-Meier method. Groups will be compared using the log-rank test. Multivariable analyses will be performed using Cox proportional hazard regression analysis.

For categorical variables, the frequency and percentages (based on the non-missing sample size) of observed levels will be reported. Bar charts will be used for graphical presentation of data. The association of a categorical outcome and categorical independent variables will be analyszed using Fishr's exact test or the χ^2 test.

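### Section 4.2 ranks two results of surgery as mandatory factors beside the intended surgical strategy, does not separate baseline from post-treatment variables, and lists neither age at diagnosis, sex nor BMI SDS at diagnosis.

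*Protocol*

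**What the plan says.** Section 4.2 divides the independent variables into mandatory and potential factors according to how strongly each is expected to influence outcome. The mandatory list holds preoperative hypothalamic involvement, irradiation and these three surgical items:

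- the intended approach: "Neurosurgical treatment strategy (intended radical resection vs" incomplete resection plus irradiation;
- the result achieved: "Realized degree of surgical resection (complete resection vs. incomplete resection");
- the damage seen afterwards: "Postsurgical hypothalamic lesions (grade 0-2").

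No demographic variable is in either list. The only age item is age at the start of growth hormone, which is not a baseline characteristic. BMI SDS appears only as an endpoint.

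Section 4.3 states the aim of investigating how treatment approaches influence survival and quality of life. It says that multivariable analyses are used "to take account of different baseline risks due to different demographic or diagnostic characteristics". Covariates may be chosen on clinical grounds or by likelihood-ratio stepwise selection, and mixed models also adjust for unnamed potential confounders. All inference is exploratory.

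**The concern.** Lesion grade and realised resection are partly produced by the strategy. The protocol's own background supplies both links of the chain. Section 2.11.1.3 says "The rate of hypothalamic dysfunction dramatically increases following radical surgical treatment", and section 3.1 says "Hypothalamic involvement resulting in radical surgical procedures and hypothalamic lesions are both clear predictors for impairments in postoperative functional capacities and QoL". A model that holds lesion grade fixed therefore compares strategies after removing the main route by which they are thought to differ. Its strategy coefficient is not the influence that section 4.3 sets out to study.

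The second gap is that section 4.3 promises demographic adjustment while section 4.2 gives it no demographic variable to use. An analyst who treats the lists as the menu for model building would never offer age at diagnosis or sex to the model. At stake is the registry's central comparison, radical versus limited surgery, on obesity and quality of life.

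**Working it through.** The protocol gives no sample size, effect size or model for this comparison, so there is no figure to reproduce. The check has three parts.

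**1. Timing of each factor.** Preoperative involvement grade is fixed before strategy is chosen. Realised resection and postsurgical lesion grade are fixed after it. Section 4.2 does not mark this difference.

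**2. Effect of conditioning on lesion grade.** In a linear model, total effect = direct effect + a × b. Here a is the shift in lesion grade caused by radical intent, and b is the change in BMI SDS per lesion grade. Adding lesion grade to the model leaves the direct effect and removes a × b. All values below are assumptions: a = 0.3 to 0.9, b = 0.5 to 1.0, direct effect 0 or 0.3. The removed part runs from 0.3 × 0.5 = 0.15 to 0.9 × 1.0 = 0.90 BMI SDS. Least-squares fits to 400,000 simulated patients per scenario, with age unrelated to strategy and outcome, agree:

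| Direct | a | b | True total | Involvement grade + age | The same + lesion grade |
|---|---|---|---|---|---|
| 0 | 0.3 | 0.5 | 0.15 | 0.14 | -0.01 |
| 0 | 0.9 | 1.0 | 0.90 | 0.90 | 0.00 |
| 0.3 | 0.3 | 0.5 | 0.45 | 0.45 | 0.30 |
| 0.3 | 0.9 | 1.0 | 1.20 | 1.20 | 0.31 |

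The simulation has no common cause of lesion and outcome other than involvement grade. The coefficient falls to zero only where the direct effect was set to zero.

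**3. The missing baseline variables.** Confounding needs a link to outcome and a link to treatment choice.

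- *Age.* For outcome, section 2.11.1.10 says that reported factors for worse quality of survival "include younger age at diagnosis and preoperative functional impairment". For treatment, section 2.9.1 makes age a consideration in decisions on reoperation or radiotherapy. Section 2.11.1.16 names age and gender as potential confounding variables in quality-of-life work. If age lowers BMI SDS by 0.3 per SD and raises the log-odds of radical intent by 0.5 per SD (both assumed), leaving it out shifts the strategy coefficient by about -0.14, for example from 0.90 to 0.76. If age is unrelated to both, the shift is nil.
- *Sex.* It is named in section 2.11.1.16, but section 2.11.1.13 calls its prognostic role unsettled, and no section links it to strategy.
- *BMI SDS at diagnosis.* Section 2.11.1.4 describes weight gain before diagnosis, "with 12 to 19% of patients reported to be obese at diagnosis". No section links it to strategy, so its case rests on precision and baseline comparability. Against a single follow-up comparison that ignores baseline, the gain is 1/(1 - r²) - 1. For an assumed r of 0.5 this is 1/0.75 - 1 = 33%, and for r of 0.7 it is 1/0.51 - 1 = 96%, expressed as equivalent extra patients. A mixed model that already holds the diagnosis value in the outcome series would not gain this much.

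**The case against.** The strongest reply is that section 4.2 fixes no adjustment set. It lists factors to be studied, ranked by expected influence, and never defines mandatory as forced jointly into every model. One mandatory item, irradiation modality and dose, is undefined for patients who were not irradiated, so a literal all-mandatory model would need coding that the protocol does not describe. Lesion grade and realised resection are proper factors when they are themselves the exposure or when the question is prognosis after surgery. Section 4.3 covers demographic characteristics and potential confounders in general terms, and a statistical analysis plan, not available here, may name the covariates. All inference is exploratory.

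Much of this stands, and it rules out three stronger readings that a reader might infer:

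- *That the protocol prescribes an over-adjusted model.* It does not. Over-adjustment is a risk that the wording leaves open.
- *That strategy estimates will remain confounded.* This is not shown. The support is best for age, weaker for sex, and for BMI SDS at diagnosis there is no stated link to treatment choice.
- *That the strategy effect would vanish, or that baseline BMI information is discarded.* The first assumes no direct effect. The second overlooks the paired tests and mixed models of section 4.3, which can use the diagnosis value.

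The objection does not remove the mismatch between sections 4.2 and 4.3. Nor does the exploratory label help, because it tempers claims about error rates and does not change what a coefficient estimates. The permitted stepwise selection adds to the risk: it tends to keep a strong outcome predictor such as lesion grade and can drop a confounder only weakly related to outcome.

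**Conclusion.** The point holds as a defect in how section 4.2 is set out and in how it fits section 4.3. Baseline and post-treatment variables share an undefined label, and the demographic covariates that section 4.3 depends on are not listed. If the mandatory factors are fitted together, or stepwise selection retains lesion grade, the strategy coefficient for BMI SDS and quality of life omits the part mediated by lesions. That conclusion rests on the causal chain the protocol itself describes. The size of the loss cannot be derived from the documents, and the range of 0.15 to 0.90 BMI SDS illustrates assumed inputs only. The point is worth correcting because it bears on the main treatment comparison and the correction is nearly free.

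**What to change.** In sections 4.2 and 4.3:

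- Label each factor as exposure, pre-treatment covariate or post-treatment variable, and say what mandatory means for model building.
- In models estimating the effect of treatment strategy, adjust only for pre-treatment variables: age at diagnosis, sex, preoperative hypothalamic grade, tumour volume, hydrocephalus, preoperative visual deficit and, at least for the BMI SDS endpoint, BMI SDS at diagnosis. Fix this set in advance and do not choose it by stepwise selection.
- Analyse realised resection and postsurgical lesion grade in separate models, described as prognosis after surgery.

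No new data item is needed. Age and anthropometry are on the assessment forms (section 5), BMI is highly recommended at primary diagnosis (section 6.2), and gender is held in the patient identification records (section 12). Hypothalamic grade, tumour volume, hydrocephalus and ophthalmological deficits are already in section 4.2. The cost is revised wording and two families of models to report instead of one.

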2.8. Treatment stategies

2.8.1. Neurosurgery

2.8.1.1. Strategies and effects

For favorably localized craniopharyngioma (i.e., without involvement of hypothalamic or optical structures), the preferred treatment of choice is an attempt at complete resection with preservation of visual and hypothalamic function [36-39]. For unfavorably localized tumors too close to or entangled with the optic nerve and/or the hypothalamus, controversy exists over whether complete resection should still be attempted or whether a planned limited resection (biopsy, partial/subtotal resection) should be performed [39-41]. Many authors take a critical view of planned radical resection in these cases because of the risk of surgically-induced deficits (mainly hypothalamic) and the high rate of recurrence in infants and small children despite apparently complete resection [42, 43]. Recurrences at ectopic locations are reported [44]. Whereas following incomplete resection the residual tumor shows progression in 71 to 90% of patients, the rate of progression after incomplete resection followed by radiotherapy is 21% [45]. Elowe-Gruau and coworkers recently published the results of a single institution study at Necker Enfants-Malades Teaching Hospital, Paris, France, showing that a hypothalamus-sparing surgical strategy combined with postsurgical radiotherapy decreased the rate of severe long-term obesity in survivors without increasing their risk for local relapses when compared with a historical cohort treated before 2002 at the same experienced institution with a radical surgical approach [46].

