However, the published literature to date [25, 42, 46-52] has not settled the controversy over the best treatment strategy for craniopharyngioma (intended primary gross total resection, versus biopsy/partial resection followed by irradiation). Therapeutic consequences of surgery and irradiation also remain a matter of debate. Above all, effects of the chosen treatment sequence (immediate irradiation vs. progression-contingent irradiation of residual tumor) on QoL are not clearly characterized based on the retrospective data published to date. A retrospective analysis sited primary therapy FSIQ (Full Scale Intelligence Quotient) losses of 9.8 points after a single complete resection compared to a loss of 1.25 points after limited resection followed by radiation therapy [52]. For a second surgical intervention carried out following a relapse, the loss was 13.1 points, statistically suggesting that radical and/or repeated surgeries seem to generate negative influences on neurocognitive functions compared to limited resection plus immediate irradiation treatment. However, only very limited available retrospective data exists.

Endoscopic procedures are usually considered in occlusive hydrocephalus caused by tumor cysts of the foramen of Monro (FOM) [53]. The small size of instruments insertable through the working canals of the endoscope allows biopsies of the tumor and prevents larger resections. The standard access is a paramedian frontal burr hole in front of the coronal suture [37]. After transcortical puncture of the lateral ventricle, the endoscope can be moved inside the inner cerebrospinal fluid (CSF) space through the FOM within some limits. Besides cyst punctures and biopsies [54], catheters can be placed under optic control.

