4.4. Treatment of missing values and outliers

For the primary analyses no imputation of missing values will be applied. Number of patients with missing data and missingness patterns will be presented descriptively. In additional sensitivity analyses multiple imputation approaches or models applicable to longitudinal data with missing values (e.g., linear mixed models) can be used. Results will be compared and discussed. In case of time-to-event enpoints missing data will be treated as right-censored.

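### The mandatory irradiation factor is defined only for irradiated patients, and in a PFS model counted from diagnosis it can take its value from the PFS event itself

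*Protocol*

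**What the plan says.** Section 4.2 heads one list "Factors of influence (mandatory") and includes in it "Irradiation: modality (photon vs. proton beam therapy) and treatment (dose"). The synopsis gives the same two modalities, and so does its German version. None of them has a level for a patient who was not irradiated. The other mandatory factors include neurosurgical strategy, which contrasts intended radical resection with incomplete resection plus irradiation. Section 4.2 counts PFS from diagnosis to progression or death, and Section 4.3 assigns multivariable time-to-event analysis to Cox regression.

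The protocol expects patients without irradiation and patients irradiated late. Section 2.8.1.1 prefers attempted complete resection for favourably located tumours and names, as an open question, the sequence "immediate irradiation vs. progression-contingent irradiation of residual tumor".

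On missing data, Section 4.4 says: "For the primary analyses no imputation of missing values will be applied". Imputation or longitudinal models appear only as optional extras ("In additional sensitivity analyses multiple imputation approaches or models applicable to longitudinal data with missing values"). It gives no rule for values that do not apply to a patient.

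**The concern.** A covariate defined only within treated patients cannot go unchanged into a model for everyone. There are two obvious ways to force it in, and both go wrong for PFS.

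- **Leave it blank for non-irradiated patients.** With no imputation and the usual deletion of incomplete rows, these patients leave any model that contains the factor. Where irradiation is given at progression, those lost are mainly the ones who stayed progression-free.
- **Add a 'none' level, or dose 0, for patients never irradiated at any time.** Nobody is lost, but the photon and proton levels now contain patients who entered them by progressing. The covariate is a consequence of the outcome.

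What is at stake is the adjusted comparison of surgical strategies on PFS, which Section 2.8.1.1 describes as unsettled. The photon–proton contrast would also mix primary with salvage irradiation.

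**Working it through.** The protocol states no sample size, power or event figure, so there is nothing to reproduce. The check asks how many patients are affected and which coding removes the problem.

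**Patients affected.** The synopsis expects 30 craniopharyngioma patients a year, so 30 × 10 = 300 over ten years. The never-irradiated share is not given. At an assumed 20%, 40% or 60%, blank coding with row deletion removes 60, 120 or 180 of the 300. A 'none' level or dose 0 removes nobody.

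**Which patients are lost.** Section 2.8.1.1 gives progression of 71 to 90% after incomplete resection, and says "the rate of progression after incomplete resection followed by radiotherapy is 21"%. Take an assumed 75 incomplete resections with irradiation only at progression. Those progression-free and not irradiated number 75 × (1 − 0.90) = 7.5 to 75 × (1 − 0.71) = 21.75, so about 8 to 22. If every progressor is irradiated, the patients who keep a modality have 100% progression instead of 71–90%.

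**Effect on the strategy hazard ratio.** Assumptions:

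- 300 patients, 30, 50 or 70% with intended radical resection.
- Exponential PFS, the same in both strategies (true hazard ratio 1), with 79% progression-free at 10 years. This places the protocol's 21% at 10 years; the protocol attaches no time point to it.
- Censoring uniform over 0–10 years.
- All limited-surgery patients irradiated up front; 20% or 40% of the radical group irradiated up front; 50% or 100% of the remaining radical-group progressors irradiated at progression.
- Photon and proton equally likely.

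The rate is λ = −ln(0.79)/10 = 0.0236 per year. The expected event share is 1 − (1 − e^(−10λ))/(10λ) = 1 − 0.21/0.2357 = 0.109.

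Among radical-group patients who ever have a modality, the event share is as follows:

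- 20% up front, all progressors irradiated: 0.109 / (0.20 + 0.80 × 0.109) = 0.109/0.287 = 38%.
- 20% up front, half of progressors irradiated: (0.20 × 0.109 + 0.80 × 0.109 × 0.5) / (0.20 + 0.80 × 0.109 × 0.5) = 0.065/0.244 = 27%.
- 40% up front, all progressors irradiated: 0.109 / (0.40 + 0.60 × 0.109) = 0.109/0.465 = 23%.
- 40% up front, half of progressors irradiated: (0.40 × 0.109 + 0.60 × 0.109 × 0.5) / (0.40 + 0.60 × 0.109 × 0.5) = 0.076/0.433 = 18%.

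The comparison group stays at 11%, although the true risk is equal. Simulated Cox models with strategy plus irradiation give these median strategy hazard ratios:

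| Coding of irradiation | 20% up front | 40% up front |
|---|---|---|
| Non-irradiated dropped | about 2.5–4.0 | about 1.5–2.4 |
| none / photon / proton, irradiation at any time | about 2.5–4.0 | about 1.5–2.4 |
| none / photon / proton, only before progression | about 0.85–1.06 | about 0.85–1.06 |

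The first two rows agree because no limited-surgery patient sits in the 'none' level under these assumptions. The strategy coefficient therefore still rests on patients with a modality. The timing of irradiation relative to progression is what matters; the missing level alone is the smaller part.

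**The case against.** A reader might infer that the plan removes every non-irradiated patient from its primary models. The documents do not say so. Not being irradiated is a known status, so the no-imputation rule does not by itself apply to it. No section codes it as missing or prescribes row deletion, and dose can be 0. Nor is the factor forced into every model: Section 4.2 says only that "the independent variables have been divided into two categories according to their expected influence on outcome and prognosis", and Section 4.3 says model selection "can be done by clinical considerations or by means of automated selection as likelihood-ratio based stepwise selection procedures". Photon versus proton can also be read as a contrast intended among irradiated patients only. All of this stands, so the loss of patients is conditional on coding and model choice.

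A reader might also infer a far larger bias. If nobody in the radical group is irradiated before progression, the same set-up gives a hazard ratio near 14. The protocol does not support that scenario: its remark on deferred irradiation concerns residual tumour, not intended radical resection. In that scenario a 'none' level leaves the figure unchanged, so it says nothing specific about the missing level. Irradiation before progression would then also coincide with strategy, and the two effects could not be separated.

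Further, coding rules are ordinary content of a statistical analysis plan, which is not at hand. That excuses the absence of a code list. It does not excuse a level set that the protocol itself fixes as two modalities in a mandatory factor. In the same list both hypothalamic factors carry an explicit grade 0 for none. Finally, Section 4.3 calls the analysis mainly descriptive and all inference exploratory. That limits the weight of the point, but Section 4.3 also aims to investigate how treatment approaches influence survival and QoL.

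**Conclusion.** The point holds in a limited form. As written, the irradiation factor is undefined for part of the cohort and, for patients irradiated at progression, is acquired through the PFS event. In a whole-cohort Cox model for PFS from diagnosis, both obvious codings bias the strategy effect against radical resection to a similar degree: about 2.5–4.0 with 20% of the radical group irradiated up front and about 1.5–2.4 with 40%, against a true hazard ratio of 1. These sizes rest on assumed irradiation shares, equal true PFS and a 10-year reading of the 21%. They show direction and mechanism and are not a forecast. The event-driven mechanism is shown for PFS only; for OS, QoL and BMI SDS what remains is the undefined value.

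The same gap affects growth hormone substitution (age at initiation, duration) and the patient load of the radiotherapy unit, neither of which has a value in untreated patients.

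**What to change.** 1. In Section 4.2 and both synopses, define irradiation as none / photon / proton. For whole-cohort PFS models, count only irradiation given before progression, or enter it as a time-dependent covariate. The time-dependent form is safer where irradiation starts well after diagnosis, because a fixed code would credit irradiated patients with event-free time they had to survive to be classified.
2. Analyse photon versus proton and dose in a separate model restricted to irradiated patients, with time from start of irradiation. Distinguish primary from salvage irradiation; for salvage patients the event is the next progression or death.
3. In Section 4.4, state that 'not applicable' (no irradiation, no growth hormone) is not a missing value.

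The cost is a few sentences and one extra model. The radiotherapy, neurosurgery and status/relapse forms listed in Section 5 suggest that no new data are needed, but the forms are not shown, so the sponsor should confirm that the start date of irradiation and the date of progression are recorded. The modality comparison will rest on fewer patients. If irradiation before progression coincides almost completely with strategy, the two effects should be reported as not separable.
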